V 2.0	06 August 2025	Substantial	Setting	Added the following blurb for Figure 1: "The data end date in Figure 1 will be updated at the time of the second, third, and final analyses, estimating data through June, September, and December 2025, respectively. All other dates shown in the figure will remain the same for the subsequent analyses"	This clarification was needed because of milestones change.
V 2.0	06 August 2025	Substantial	Annex 2	Code J9415 changed to J9145	while reviewing codes it was noticed a typo in the 'CD38 mAbs' and 'mAbs' codes under Annex 2. It looks like the code J9415 should actually be J9145 for Daratumumab.

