9.3. Variables

Table 1 includes definitions and assessment periods for all study variables that will be used as eligibility criteria. The full code list can be found in ANNEX 2. ADDITIONAL INFORMATION.

Table 1. Variables Used to Determine Eligibility

Variable	Operational Definition	Assessment Period
Elranatamab	Prescription claim or medical claim with a National Drug Code (NDC), Healthcare Common Procedure Coding System (HCPCS), International Classification of Diseases, 10th Edition (ICD-10) code or generic name in the inpatient, non-inpatient or pharmacy setting for elranatamab	Index event
Teclistamab	Prescription claim or medical claim with an NDC, HCPCS, ICD-10 code or generic name in the inpatient, non-inpatient or pharmacy setting for teclistamab	Index event
Age	Age is greater than or equal to 18 years and is not missing	Index date
MM diagnosis	Medical claim in the inpatient or non-inpatient setting with an ICD-10 code for MM	All available data to index date
Observability	Closed-claims medical and pharmacy enrollment	180 days prior to index date to index date (inclusive) and 30 days post index
Medicare entitlement	Reason for Medicare entitlement	Index date

Table 2 includes definitions and assessment periods for all study variables that will be used as baseline and treatment characteristics. The full code list can be found in ANNEX 2. ADDITIONAL INFORMATION. If applicable, the frequency and percentage of patients with missing data for each variable will be described.

Table 2. Variables Used to Determine Baseline and Treatment Characteristics

Objective	Variable	Definition	Assessment Period(s)
1	Age	Age in years (continuous). Age will be calculated using the birth year variable from the beneficiary enrollment information.	Index date
1	Sex (assigned at birth)	Categorical sex	Index date
1	Race/Ethnicity	Beneficiary enhanced race/ethnicity designation based on first and last name algorithms and the Social Security Administration race code (modified using the Research Triangle Institute algorithm). Categorical race and ethnicity Caucasian African American Asian or Pacific Islander Hispanic or Latino Other Unknown	Index date
1	US Census Region	Categorical region, assessed as the most recent value from index date Northeast Midwest West South Unknown	Index date
1	State	State of residence	Index date

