1	Rheumatic disease	Medical claim with an ICD-10 code in the inpatient or non-IP setting for rheumatic disease (dichotomous)	180 days prior to index date to index
1	Peptic ulcer disease	Medical claim with an ICD-10 code in the inpatient or non-IP setting for peptic ulcer disease (dichotomous)	180 days prior to index date to index
1	Liver disease	Medical claim with an ICD-10 code in the inpatient or non-IP setting for liver disease (dichotomous)	180 days prior to index date to index
1	Diabetes	Medical claim with an ICD-10 code in the inpatient or non-IP setting for diabetes (dichotomous)	180 days prior to index date to index
1	Renal disease	Medical claim with an ICD-10 code in the inpatient or non-IP setting for renal disease (dichotomous)	180 days prior to index date to index date
1	Hemiplegia or paraplegia	Medical claim with an ICD-10 code in the inpatient or non-IP setting for hemiplegia or paraplegia (dichotomous)	180 days prior to index date
1	Human immunodeficienc y virus	Medical claim with an ICD-10 code in the inpatient or non-IP setting for human immunodeficiency virus (dichotomous)	180 days prior to index date to index date

Objective	Variable	Definition	Assessment Period(s)
1	Metastatic solid tumor	Medical claim with an ICD-10 code in the inpatient or non-IP setting for metastatic solid tumor (dichotomous)	180 days prior to index date to index date

Table 3 includes definitions and assessment periods for all study variables being used as outcomes. The full code list can be found in ANNEX 2. ADDITIONAL INFORMATION. If applicable, the frequency and percentage of patients with missing data for each variable will be described.

Table 3. Key Variables of Interest

Objective	Variable	Definition	Assessment Period(s)
Treatment ex	posure		
2	Use of supportive MM medications	Medical or pharmacy claim with evidence of an NDC, HCPCS, generic name or CPT code for the following medications (dichotomous):	Index date to the end of follow-up Index date Step-Up Dosing Period Maintenance Periods
2	Reported vial size	Reported vial size in the following categories (categorical): • Unknown vial – inpatient dose • 44mg/1.1mL • 76mg/1.9mL • Missing dose/unknown dose For the cohort of teclistamab patients the reported vial size (categorical): • Unknown vial – inpatient dose • 30mg/3mL • 153mg/7mL • Missing dose/unknown dose	Index date to the end of follow-up Index date Step-Up Dosing Period Maintenance Periods

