ANNEX 2. ADDITIONAL INFORMATION

			Codes
Variable	Role	Data Source(s)	
Elranatamab	Inclusion criteria	Claims data	HCPCS: C9165, J1323 NDC: 00069449401, 00069449402, 00069252201, 00069252202 ICD-10 Procedure code: XW013L9 Generic name: Elranatamab
Teclistamab	Inclusion criteria	Claims data	HCPCS: J9380, C9148 NDC: 57894044901, 57894045001 ICD-10 Procedure code: XW013487Generic name: Teclistamab
Multiple Myeloma	Inclusion criteria, Outcome - HCRU	Claims data	C90.0x
Age	Inclusion criteria, Baseline characteristic - Demographic	Claims data	N/A
Sex	Baseline characteristic - Demographic	Claims data	N/A

Dagg/Etlan! -: t	Baseline	Claims	N/A
Race/Ethnicity	characteristic - Demographic	data data	N/A
US Census Region	Baseline characteristic - Demographic	Claims data	N/A
State	Baseline characteristic - Demographic	Claims data	- N/A
BCMA-directed therapy	Baseline characteristic - Treatments, Outcome - HCRU	Claims data	CPT: 0537T, 0538T, 0539T, 0540T HCPCS: C9081, C9098, Q2055, Q2056, J9037, C9069 NDC: 57894011101, 57894011102, 59572051501, 59572051502, 59572051503, 00173089601 Generic names: Idecabtagene Vicleucel, Ciltacabtagene Autoleucel, Belantamab ICD10PCS: XW033K7, XW043K7, XW043A7, XW043A7, XW033A7
CAR-T	Baseline characteristic - Treatments, Outcome - HCRU	Claims data	CPT: 0537T, 0538T, 0539T, 0540T HCPCS: C9081, C9098, Q2055, Q2056 NDC: 57894011101, 57894011102, 59572051501, 59572051502, 59572051503 Revenue codes: 0871, 0872, 0873, 0874, 0891 ICD10PCS: XW033C7 XW033G7 XW033J7 XW033K7 XW043C7 XW043G7 XW043K7 Generic names: Idecabtagene Vicleucel, Ciltacabtagene Autoleucel
Hematopoietic stem cell transplantation	Baseline characteristic - Treatments	Claims data	CPT: 38240, 38241, 38242, 38243 HCPCS: A52879, S2150 ICD-10 Diagnosis: T86.0, T86.00, T86.01, T86.02, T86.03, T86.09, T86.5, Z48.290, Z94.81, Z94.84 ICD-10 Procedure: 30240Y0, 30243Y0, 30250Y0, 30253Y0, 30260Y0, 30263Y0, 30230Y1, 30233Y1, 30240Y1, 30243Y1, 30230Y2, 30233Y2, 30240Y2, 30243Y2, 30230Y3, 30233Y3, 30240Y3, 30243Y3, 30230Y4, 30233Y4, 30240Y4, 30243Y4, 30253Y1, 30260Y1, 30263Y1, 30233X0,

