Talquetamab	Baseline characteristic - Treatments, Outcome - HCRU	Claims data	30233G0, 30233G1, 30233G2, 30233G3, 30233X1, 30233X2, 30233X3, 30233X4, 30233Y0, 30243X0, 30243G0, 30243G1, 30243G2, 30243G3, 30243X1, 30243X2, 30243X3, 30243X4, 0243Y4, 30283X0, 30283G0, 30283G1, 30283G2, 30283G3, 30283X1, 30283X2, 30283X3, 30283Y4, 30283Y1, 30283Y2, 30283Y3, 30283Y4 HCPCS: C9163 NDC: 57894046901, 57894047001 Generic name: Talquetamab
Proteasome inhibitors	Baseline characteristic - Treatments, Outcome - HCRU	Claims data	HCPCS: C9295, J9041, J9044, J9046, J9047, J9048, J9049, S0115 NDC: 00143909801, 00409170001, 00409170301, 00409170401, 00781325870, 10019099101, 25021024410, 43598042660, 43598086560, 50742048401, 51817058601, 55150033701, 60505605004, 63020004901, 63020007801, 63020007802, 63020007901, 63020007902, 63020008001, 63020008002, 63323082110, 68001053436, 68001054036, 68001054136, 70511016105, 70511016202, 70710141101, 70771170801, 70860022510, 71288011810, 72205018301, 72266024301, 76075010301, 83090000801 Generic names: Bortezomib, Carfilzomib, Ixazomib
Immunomodulatory drugs	Baseline characteristic - Treatments, Outcome - HCRU	Claims data	NDC: 00378193501, 00378193528, 00378193601, 00378193628, 00378193701, 00378193728, 378194001, 00378194021,00 00378194101, 00378194121, 00378194201, 00378194221, 00480124128, 00480124228, 00480124328, 00480124421, 00480124521, 00480124621, 31722025701, 31722025728, 31722025801, 31722025828, 31722025901, 31722025928, 31722026001, 31722026021, 31722026101, 31722026121, 31722026201, 31722026221, 43598051101, 43598051163, 43598051201, 43598051201, 43598051521, 43598051301, 43598051501, 43598051521, 43598051601, 43598051663, 47781048401, 47781048401, 47781048528, 47781048401, 4778104877, 47781048801, 47781048877, 59572020594, 59572020597, 59572021015, 59572021095, 59572021513, 59572021593,

			50572022016 50572022006 50572040200

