			Tigecycline, Clindamycin, Lincomycin, Spectinomycin, Gentamicin, Cefpodoxime, Linezolid, Rifabutin, Gatifloxacin, Amikacin, Kanamycin, Cefadroxil, Cephapirin, Sulfanilamide, Sulfacetamide, Chloramphenicol, Dapsone, Polymyxin, Nalidixic Acid, Mafenide, Lomefloxacin, Mezlocillin, Ciprofloxacin, Ciprofloxacin Lactate, Moxifloxacin, Clofazimine, Mupirocin, Ticarcillin, Cefotetan, Cefotaxime, Silver Sulfadiazine, Levofloxacin, Oxytetracycline, Cefoperazone, Trovafloxacin Mesylate, Clarithromycin, Tinidazole, Ofloxacin, Doripenem, Sulfathiazole, Rifampin, Chloramphenicol Sod Succinate, Meropenem, Azithromycin, Cefdinir, Paromomycin, Colistin, Enoxacin, Sparfloxacin, Quinupristin, Netilmicin, Ceftibuten, Cefprozil, Rifapentine, Telithromycin, Daptomycin, Furazolidone, Bismuth Subsalicylate, Grepafloxacin, Piperacillin, Cefditoren, Ceftaroline Fosamil, Fosfomycin Tromethamine, Telavancin, Polymyxin B Sulfate, Gemifloxacin, Rifaximin, Sarecycline, Bacitracin, Chloramphenicol Palmitate, Chlortetracycline, Trimethoprim, Aminosalicylic, Pretomanid, Bacitracin Zinc, Fidaxomicin, Colloidal Bismuth Subcitrate, Omeprazole, Rifamycin, Dalbavancin, Cefiderocol, Bedaquiline, Oritavancin, Ceftolozane, Tedizolid, Plazomicin, Ozenoxacin, Delafloxacin Meglumine, Triamcinolone, Omadacycline, Eravacycline, Lefamulin, Ivermectin, Salicylic Acid
Antifungals	Baseline characteristic - Treatments	Claims data	HCPCS: J0285, J0286, J0287, J0288, J0289, 80285, J3465, J1450, J2248, J1835, J0637, J0348
			Generic name (and associated NDC codes): Amphotericin B, Voriconazole, Natamycin, Fluconazole, Micafungin, Posaconazole, Itraconazole, Caspofungin, Anidulafungin, Isavuconazole, Nystatin
Intravenous	Baseline	Claims	CPT: 90283
immunoglobulin	immunoglobulin characteristic - Treatments	data	HCPCS: C9072, C9130, C9270, G0332, J1459, J1554, J1556, J1557, J1566, J1568, J1572, J1576, J1599, Q4087, Q4088, Q4091, Q4092, Q4097, Q9941, Q9942, Q9943, Q9944
			ICD-10 Procedure: 30233S1, 30243S1, 30253S1, 30263S1
			NDC: 00026064012, 00026064020, 00026064071, 00026064512, 00026064515,

00026064520, 00026064524, 0002606 00026064612, 00026064620, 0002606 00026064625, 00026064671, 0002606	-
	64624. I
00026064625, 00026064671, 0002606	-
	64812,
00026064815, 00026064820, 0002606	64871,
00026064912, 00026064920, 0002606	64924,
00026064971, 00069101101, 0006910	01102,
00069110901, 00069110902, 0006912	22401,
00069122402, 00069131201, 0006913	31202,
00069141501, 00069141502, 0006915	55801,

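### Annex 2 prints the teclistamab ICD-10 procedure code with eight characters, so inpatient doses identifiable only by that code would be missed

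*Protocol*

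**What the plan says.** - Annex 2, Teclistamab row (role: inclusion criteria) lists two HCPCS codes (J9380, C9148), two NDCs, and then "ICD-10 Procedure code: XW013487Generic name: Teclistamab". The Elranatamab row gives "ICD-10 Procedure code: XW013L9 Generic name: Elranatamab".
- Section 9.3, Table 1 lets teclistamab be identified by an NDC, an HCPCS code, or an "ICD-10 code or generic name in the inpatient, non-inpatient or pharmacy setting for teclistamab". These are alternatives; any one suffices.
- Section 9.2 sets the index date at the first elranatamab or teclistamab claim after the myeloma diagnosis. Section 9.7.2, Table 5 runs the teclistamab step-up window from index to Day 7, with three administrations expected.
- Section 9.3, Table 3 plans a vial-size category "Unknown vial – inpatient dose" for both drugs.
- Section 9.2.2 excludes anyone who received both drugs. Section 9.2.1 requires a teclistamab-free period for patients treated before 14 August 2023.
- Section 9.8 says cohorts are coded from the codes in the protocol, which is to be followed strictly.
- Section 5 records that another code in this annex was corrected in V2.0: "Code J9415 changed to J9145".

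**The concern.** A code list that defines a cohort has to match the claims it is run against. The printed teclistamab procedure code does not have the format of the other procedure codes in the annex, and Section 9.8 makes the annex operative rather than illustrative. Procedure codes would matter most for doses given in hospital, and the vial-size category shows that the plan expects some inpatient doses without product-level vial detail.

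If a teclistamab start in hospital is visible only through its procedure code, the printed string misses it. The first later claim found by another route then becomes the index date, and everything anchored on index moves with it: the step-up window and its RAI, the care setting at index, and the start of adverse-event follow-up. A patient with no later claim does not enter the cohort. The matching elranatamab code is well formed, so the two drugs would not be identified equally well.

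**Working it through.** **1. Format check within the annex.** Every ICD-10 procedure entry in Annex 2 was counted by number of characters.

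| List | Entries | Seven characters | Exceptions |
|---|---|---|---|
| Elranatamab | 1 | 1 | none |
| Teclistamab | 1 | 0 | XW013487 (8) |
| BCMA-directed therapy | 5 | 5 | none |
| CAR-T | 7 | 7 | none |
| Stem cell transplantation | 58 | 57 | 0243Y4 (6) |
| Intravenous immunoglobulin | 4 | 4 | none |
| Total | 76 | 74 | 2 |

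The CAR-T list ("ICD10PCS: XW033C7 XW033G7 XW033J7 XW033K7 XW043C7 XW043G7 XW043K7") and the immunoglobulin list ("ICD-10 Procedure: 30233S1, 30243S1, 30253S1, 30263S1") show the seven-character form plainly. The only other irregular entry ("0243Y4, 30283X0") is in a baseline variable; XW013487 is the only irregular entry that defines a cohort.

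**2. Can the intended code be recovered?** Deleting one character gives eight different seven-character strings. Requiring the XW013 stem of the elranatamab code leaves three: XW01387, XW01347 and XW01348. The protocol does not say which is meant, and a shared stem is itself an assumption.

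**3. Who would be affected?** Let p be the share of teclistamab patients who start in hospital, and q the share of those whose stay carries no HCPCS, NDC or generic-name identifier. The share indexed late or lost is s = p × q. The protocol gives neither p nor q. With assumed p of 30%, 60% or 90%:
- q = 0 gives s = 0 in each case;
- q = 1 gives s = 30%, 60% or 90%.

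The upper values assume the very point that is unknown.

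**4. What would happen to such a patient?**
- Step-up RAI: suppose all three step-up doses are in hospital and unseen, and dosing is weekly afterwards. With index counted as Day 1, the next weekly dose falls on Day 8, outside the window, so RAI is 1/3 = 0.33 instead of 3/3 = 1. If index is Day 0, a dose on Day 7 is also counted and RAI is 2/3 = 0.67.
- CRS and ICANS: Table 3 counts both from the index date, so events during an unseen hospital step-up fall before follow-up. For CRS, a 30-day washout can also remove the patient from incident cases. Table 3 attaches no washout footnote to ICANS.
- Elranatamab cohort: a patient whose teclistamab dose is unseen stays in, although Section 9.2.2 would exclude them, and the switch is not recorded as a bispecific next treatment.

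**The case against.** The tempting stronger reading is that inpatient teclistamab starts are missed as a rule and that index dates slip past step-up. The protocol does not support that. Table 1 gives three other routes and applies them to inpatient claims too. The unknown-vial category says only that vial size may be missing for an inpatient dose, not that HCPCS code, NDC and generic name are all absent. This objection stands, and it makes the consequence conditional.

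The extra character may also be a PDF extraction fault. In the extracted text, the code runs into the next words without a space, and damaged labels and digit strings occur elsewhere in the annex. A lost space does not by itself explain an extra digit, so the doubt calls for a look at the source rather than dismissal.

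Three further points limit the stakes:
- The teclistamab cohort serves Exploratory Objective 3, and Section 9.7 reports each cohort separately without formal comparison.
- Some early deaths would probably drop out whatever the code, because Section 9.2.1 requires 30 days of enrolment after index.
- The label given to the J9145 correction shows nothing about materiality, since every row of the V2.0 log is marked substantial. It does show that the sponsor corrects errors of this kind.

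**Conclusion.** The point holds in conditional form. As printed, the teclistamab procedure code has the wrong length for its type and would match no seven-character procedure claim under exact matching. This is a flaw in an operative, cohort-defining list. Its effect is confined to inpatient doses identifiable by procedure code alone, a share that the protocol does not give and that could be nil. Where it occurs, index dating, step-up RAI, index care setting and early CRS and ICANS capture are wrong for that patient, and the both-drugs exclusion and bispecific next-treatment events in the elranatamab cohort may be touched as well.

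The conclusion assumes that the eight characters are in the source document, that matching is exact, and that the program follows the annex as printed. It is not a finding that teclistamab results already delivered are wrong.

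**What to change.** 1. Check the code in the source document. If it has eight characters there, replace it with the seven-character code confirmed in the official code set; it cannot be derived from the protocol.
2. Check whether the executed program used the printed string. If it used a valid code, correcting the annex is enough.
3. Only if it used the printed string, re-run teclistamab identification and index dating and re-apply the both-drugs exclusion. Report how many patients were added, re-dated or excluded, and disclose the effect on interim tables already delivered.
4. Verify the six-character transplantation entry in the same pass.

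The cost is one annex correction and a program check, plus a re-run if needed. The V2.0 milestones place two interim analyses and the final analysis (27 February 2026) after the V2.0 date of 6 August 2025, so the correction can be carried into the final results.

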1	Care setting	Categorical care setting for elranatamab or teclistamab administration Inpatient (IP) Non-IP Pharmacy	Index date, second treatment date, third treatment date, and overall

Objective	Variable	Definition	Assessment Period(s)
1	Time since MM diagnosis	Time (in months) from first MM diagnosis to index date (continuous)	MM diagnosis to index date
1	Income	Categorical household income	Index date
1	Education	Categorical level of highest education completed:	Index date
1	Marital Status	Categorical marital status:	Index date
1	Home Ownership	Categorical home ownership status: Renter Owner Unknown	Index date
1	Triple class exposed ¹⁷	 Medical claim in the IP, Non-IP or pharmacy setting with an NDC, HCPCS, Current Procedural Terminology (CPT), generic name, or ICD-10 procedure code for all the following therapies in the inpatient, non-IP, or pharmacy setting (dichotomous): ≥ 1 claim for PIs (see generic names below) ≥ 1 claim for IMiDs (see generic names below) ≥ 1 claim for CD38 mAbs (generic names: daratumumab, isatuximab) 	MM diagnosis to 1 day prior to index date
1	Penta-drug exposed ¹⁷	Medical claims with an NDC, HCPCS, CPT, generic name, or ICD-10 procedure codes in the inpatient, non-IP or pharmacy setting for all of the following therapies(dichotomous): • ≥ 2 distinct claims for PIs (see generic names below) • ≥ 2 distinct claims for IMiDs (see generic names below) • ≥ 1 claim for CD38 mAbs (generic names: daratumumab, isatuximab)	MM diagnosis to 1 day prior to index date

Objective	Variable	Definition	Assessment Period(s)
1	Hematopoietic Stem Cell Transplantation	Medical claim with an HCPCS, CPT, or ICD-10 code for hematopoietic stem cell transplantation in the inpatient, non-IP setting (dichotomous)	MM diagnosis to 1 day prior to index date
1	BCMA-directed therapy	Medical claim with an NDC, HCPCS CPT, generic name or ICD-10 procedure code in the inpatient, non-IP, or pharmacy setting for idecabtagene vicleucel, ciltacabtagene autoleucel, or belantamab (dichotomous)	MM diagnosis to 1 day prior to indexhe date Index date to the end
			of follow-up
1	CAR-T	Medical claim with an NDC, HCPCS, generic name or CPT code in the inpatient, non-IP, or pharmacy setting for idecabtagene vicleucel or ciltacabtagene autoleucel (dichotomous)	MM diagnosis to 1 day prior to index date
		autoreucer (dienotomous)	Index date to the end of follow-up

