Exploratory Obj 1	Other infectious hepatitis ²	Medical claim with an ICD-10 code in the inpatient, non-IP or pharmacy setting for infectious hepatitis (other than hepatitis B or C) (dichotomous)	Index date to end of follow-up, where follow-up will be based on last dose of elranatamab or teclistamab (e.g., 14 days after last recorded dose or 90 days after last recorded dose).
Exploratory Obj 1	Helicobacter pylori ²	Medical claim with an ICD-10 code in the inpatient, non-IP or pharmacy setting for helicobacter pylori (dichotomous)	Index date to end of follow-up, where follow-up will be based on last dose of elranatamab or teclistamab (e.g., 14 days after last recorded dose or 90 days after last recorded dose).

Exploratory Obj 1	Candida esophagitis ²	Medical claim with an ICD-10 code in the inpatient, non-IP or pharmacy setting for candida esophagitis (dichotomous)	Index date to end of follow-up, where follow-up will be based on last dose of elranatamab or teclistamab (e.g., 14 days after last recorded dose or 90 days after last recorded dose).				
Exploratory Obj 1	Urinary tract infection ²	Medical claim with an ICD-10 code in the inpatient, non-IP or pharmacy setting for a urinary tract infection (dichotomous)	Index date to end of follow-up, where follow-up will be based on last dose of elranatamab or teclistamab (e.g., 14 days after last recorded dose or 90 days after last recorded dose).				
Exploratory Obj 1	Time to infection onset	Time in days from index date to first infection for the following infections:	Index date until censor				
Effectiveness	Effectiveness						
Exploratory Obj 2	os	Time (in months) from index date until date of death (continuous)	Index date until censor				
Exploratory Obj 2	TTNT/D	Time (in months) from index date until the date of the next treatment (CAR-T, BsABs, bendamustine or belantamab) or death (continuous)	Index date until censor				

- 1. Variable will be measured as incident and prevalent. Incident cases have 30-day washout period applied
- 2. Variable will be measured as incident and prevalent. Incident cases have 60-day washout period applied
- 3. Variable will be measured as incident and prevalent. Incident cases have 14-day washout period applied

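### Annex 2 accepts codes for cell collection and preparation as receipt of CAR-T, so next treatment can be dated early and patients never infused can be counted as treated

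*Protocol*

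**What the plan says.** Table 2 (Section 9.3) makes CAR-T a yes/no variable, before index and again during follow-up, tied to two products: a claim "for idecabtagene vicleucel or ciltacabtagene autoleucel (dichotomous"). The code types it admits are NDC, HCPCS, generic name and CPT.

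The only operational list is in Annex 2. The CAR-T row gives "CPT: 0537T, 0538T, 0539T, 0540T", then four HCPCS codes, then NDC codes, then "Revenue codes: 0871, 0872, 0873, 0874, 0891", then ICD-10 procedure codes and generic names. The BCMA-directed therapy row opens with "CPT: 0537T, 0538T, 0539T, 0540T HCPCS: C9081, C9098, Q2055, Q2056, J9037, C9069" and has no revenue codes. Neither row prints descriptors, ranks the codes or says which claim dates the treatment.

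CAR-T then feeds the outcomes. In Table 3, TTNT/D runs to the "date of the next treatment (CAR-T, BsABs, bendamustine or belantamab) or death". The same set of next treatments defines discontinuation (Table 3; Section 9.7.5). It also censors treatment exposure, HCRU and cost, RAI and tolerability (Sections 9.7.2, 9.7.3, 9.7.4 and 9.7.6). Section 9.3 names Annex 2 as the full code list for Tables 1 to 3, and Section 9.8 has the measures coded from the protocol's codes and algorithms.

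**The concern.** Read by standard nomenclature, 0537T is harvest of T lymphocytes, 0538T preparation for transport, 0539T receipt and preparation, and 0540T administration. Revenue codes 0871 to 0873 cover cell collection and processing. Harvesting cells is not the same as receiving the product: it comes before infusion and need not lead to one. A list that treats the first step and the last as equivalent lets a pre-infusion claim stand in for the infusion.

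Three things are then at stake. The next-treatment date can fall before the treatment. Index-drug doses, costs and adverse events after a collection claim can drop out through censoring. A patient collected but never infused can be reported as a switcher or, if collected before index, as having had prior CAR-T. TTNT/D and adverse events are exploratory, but treatment history, administration and HCRU/cost belong to primary Objectives 1 to 3 (Section 8).

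**Working it through.** The protocol states no figure that depends on this list, so there is nothing to reproduce. The check is a comparison of the text, followed by scale calculations on assumed inputs.

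**1. Definition against list.**
- Table 2 requires a claim for one of two named products. Those products already have their own HCPCS, NDC and generic-name entries. The CPT and revenue codes name no product, so they identify services.
- Table 2's CAR-T entry admits neither revenue codes nor ICD-10 procedure codes; Annex 2 lists both.
- By Table 2, CAR-T (two products) is a subset of BCMA-directed therapy (the same two plus belantamab). In Annex 2 the CAR-T row holds five revenue codes and XW033C7, XW033G7, XW033J7, XW043C7 and XW043G7, none of which is in the BCMA-directed row. A patient can therefore be CAR-T yes and BCMA-directed no, which the definitions rule out.

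**2. Shift for one affected patient.** Months = days / 30.4375 (Section 9.7.5). The collection-to-infusion lag is assumed.
- 28 / 30.4375 = 0.92
- 42 / 30.4375 = 1.38
- 60 / 30.4375 = 1.97

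**3. TTD under its two definitions.** Take an invented record: collection claim on day 90, last index dose on day 125, infusion on day 135.
- Table 3 measures to the last administration before discontinuation. The end point moves from a dose on or before day 90 to day 125, at least 35 days (35 / 30.4375 = 1.15 months). Had no index dose followed day 90, TTD would not change.
- Section 9.7.5 measures to the date of discontinuation. If that is the next-treatment date, it moves from day 90 to day 135, or 45 days (45 / 30.4375 = 1.48 months).

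**4. Cohort median TTNT/D.** Simulation of 400,000 patients without censoring. All inputs are assumed: exponential times with median 6 or 12 months; CAR-T 5% to 30% of events; lag 2 to 8 weeks (0.46 to 1.84 months); 0% or 10% of collected patients never infused, each given a false event at a uniformly random earlier time.

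| True median | CAR-T share | Lag | Fall, lag only | Fall, 10% never infused |
|---|---|---|---|---|
| 6 | 5% | 2 wk | 0.02 | 0.05 |
| 6 | 15% | 4 wk | 0.13 | 0.21 |
| 6 | 30% | 8 wk | 0.51 | 0.66 |
| 12 | 30% | 8 wk | 0.53 | 0.84 |

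Falls are in months, and the full grid runs from 0.02 to 0.84. As a cross-check, the lag-only fall should be near share × lag: 0.05 × 0.46 = 0.02 and 0.30 × 1.84 = 0.55, which agrees.

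**5. Yes/no variables.** Section 9.5 reports 133 patients with an elranatamab claim as of August 2024. On that count, one wrongly labelled patient moves the prior-CAR-T percentage by 1 / 133 = 0.75 percentage points.

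**The case against.** The strongest objection is that Annex 2 prints bare codes, so their meaning comes from outside the protocol. That stands as a caution, and the sponsor should confirm the descriptors. But looking up what a plan's own codes denote in their code set is reading the plan, and the mismatch of code types in step 1 needs no descriptors.

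Second, the role column for the CAR-T row names only baseline treatment and HCRU. Annex 2 has no separate next-treatment row, however. The rows holding belantamab and bendamustine carry the same role label, and both drugs are next-treatment events.

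Third, Section 9.7 leaves detailed methods to the SAP, and a dating rule is ordinary SAP content. Yet the protocol has already fixed which codes count, Section 9.8 says it will be strictly followed, and version 2.0 made code changes by amending Annex 2.

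Fourth, the effect is not shown to occur. This largely stands. A reader might infer that every CAR-T switch is dated weeks too early, or that collected-but-not-infused patients are a known group in these data. The documents do not support that. They do not say whether pre-infusion services are billed separately on earlier dates, how long the interval is, or how many patients are never infused.

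**Conclusion.** The point holds as a defect in the code list. Followed literally, Annex 2 lets a pre-infusion service count as receipt of CAR-T, and Table 2 and Annex 2 disagree on the accepted code types.

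The consequence is conditional on such services being billed on their own earlier dates. Where they are, the error runs one way: TTNT/D shorter, follow-up cut early, CAR-T use overstated. Nor does it follow that TTD is shortened for every affected patient. Under Table 3 it changes only where index doses follow the collection claim; under Section 9.7.5 the effect is broader.

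For an affected patient the date moves by 0.9 to 2.0 months on an assumed lag of 28 to 60 days. The cohort median TTNT/D probably moves by less than 1 month, on assumed medians, CAR-T shares, lags and non-infusion rates. The effect on the median is therefore modest. The case for correcting it rests more on individual event dates, censoring and prior-CAR-T status in a small cohort.

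**What to change.** In Annex 2, annotate each CAR-T code with its descriptor and mark which codes establish receipt. For exposure status, the next-treatment event and censoring dates, count only administration and product codes: CPT 0540T, the infusion and product revenue codes (0874 and 0891, subject to the sponsor's confirmation), the product HCPCS, NDC and generic-name entries, and the ICD-10 procedure codes for infusion. Remove 0537T to 0539T from the receipt definition in both rows and 0871 to 0873 from it in the CAR-T row; keep them for HCRU if wanted. State that the date of receipt is the date of the first qualifying claim.

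Amend Table 2 so that its CAR-T entry admits the code types Annex 2 retains, and make the CAR-T codes a subset of the BCMA-directed codes. Because TTD depends on it, settle whether Table 3 or Section 9.7.5 defines its end point.

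The cost is an edit to Annex 2 and Table 2 and a re-run of the affected outputs, with no new data. A count of patients whose only CAR-T claim is a pre-infusion code, and of the days between the two kinds of claim, would replace the assumptions above with observed values, subject to the CMS cell-size rule.
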